3 DATA SOURCE

Motor assessments:

Step Activity Monitor (SAM): These small activity monitors measure an individual's number of steps during real world activities. The ankle strap of the SAM will be attached to the least affected limb and should be positioned on the inside (medial) aspect just above the anklebone. It should be worn over a sock, so as not to be rubbing on skin, and the arrow on the front of the monitor should be pointing up. The number of steps and number of minutes in which participants walk greater than 100 steps per minute per day (moderate intensity minutes) over the 7-day period at each time point will be used in analyses.

Six-Minute Walk Test (6MWT): This is a measure of the distance a participant walks in a six-minute time period. The six-minute walk test is a safe, simple, and useful measure of walking ability in patients with Parkinson's disease. The test will be carried out on level, obstacle-free enclosed corridors. Each participant will be instructed to cover as much ground as possible on foot in six minutes. A tester will accompany the participant, acting as a timekeeper and guarding the participant as needed. This test takes about 10 minutes to administer. Greater distances indicate increased ability for community ambulation.

Ten-Meter Walk Test (10MWT): This is a measure of gait speed. The test includes an initial two meter acceleration phase, followed by six meters of ambulation, and finished

STATISTICAL ANALYSIS PLAN – WHIP-PD

with a two meter deceleration phase. Each of the distances mentioned will be marked for accuracy, and only the middle six meters will be timed. Each participant will be instructed to walk at a comfortable walking pace (2 trials). A tester will accompany the participant, acting as a timekeeper and guarding the participant as needed.

4 ENDPOINTS AND COVARIATES

Endpoints

The primary outcomes are the change from baseline to one year in mean number of steps per day over a seven-day period (via SAM) and the number of moderate intensity minutes (number of minutes with greater than 100 steps) for the mHealth compared to active exercise control participants.

Secondary outcome is the change from baseline to one year in walking capacity. Walking capacity will be the number of meters walked during the 6MWT and meters per second for the 10MWT.

5 HANDLING OF MISSING VALUES OR OTHER DATA CONVENTIONS

Missing data

Vigorous attempts will be made to obtain follow-up assessments on all participants, regardless of compliance with treatment protocols. If a participant cannot complete any of the follow-up assessments, the reason will be clearly documented.

Non-normal data

Distributions will be examined to determine the need for data transformation, winsorizing, or nonparametric analyses.

6 STATISTICAL PROCEDURES

Primary Outcome Analyses

Our primary aim is to determine effectiveness of the intervention to improve walking behavior at one year. We will conduct the main analyses on the full sample and compare SAM data for change from baseline to one year in (1a) mean number of steps per day and (1b) number of minutes in which participants walk greater than 100 steps per minute per day (moderate intensity minutes) over a seven-day period for the mHealth versus active exercise control participants.

STATISTICAL ANALYSIS PLAN – WHIP-PD

The unadjusted treatment comparison will be determined using a Satterthwaite unpooled t-test to allow for unequal variance in treatment groups.

The two-sided 0.05 level will be used for significance in all analyses.

Secondary Outcome Analyses

We will use a similar approach to the analysis described above to analyze the effect of the intervention on secondary outcomes of walking capacity (6MWT and 10MWT).

Each hypothesis will be tested two-sided (level of significance of 0.05).

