Physical Activity: Physical activity will be measured during a one-week period following each of the 4 assessment sessions using the StepWatch™ Activity Monitor (SAM). Subjects will wear the unobtrusive StepWatch 4 Activity Monitor (SAM, Modus Health, Edmonds, WA,), 24 hours per day for 7 days, except when bathing, showering, or swimming. The SAM is approximately the size of a pager, weighs 38g, and is attached using Velcro closures immediately proximal to the lateral malleolus of either leg. Study personnel will log pertinent setup information (start time, height, weight etc) on the SAM Setup form. The SAM is a small, waterproof, highly durable, self-contained device that is worn on the ankle and records the number of strides taken every minute. The SAM uses a combination of acceleration, position, and timing to detect steps taken with the leg of attachment. It is designed for long-term use during daily activities performed in an individual's customary environment over hours or days without maintenance by the user. Data are recorded as a temporal series of counts, with each data point represents the number of steps per one-minute interval. Step counts will be summed across days. In the rare event that the SAM device is returned after the 7 day wearing period and the data is unusable or the device has been damaged, the participant may be asked to wear an alternate SAM device for another 7 consecutive days.

The SAM will continuously monitor the number of steps taken over 7-days between the assessment period (after consent), but before the initiation of the intervention. The primary

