2 ANALYSIS SETS/POPULATIONS/SUBGROUPS

Sample size

Steps per day via SAM: In our pilot study, low activity participants in the mHealth group had 6028 (SD 1046) steps per day at baseline and 6918 (1900) at 12 months. Participants in the active control group had 6330 (SD 560) steps per day at baseline and 6788 (SD 1636) at 12 months.¹ Using the Two-Sample T-Test Allowing Unequal Variance Procedure in PASS Power Analysis and Sample Size software, group sample sizes of 61 participants per group will be needed to achieve 80% power, $\alpha = .05$. To account for 20% drop out rate, 74 participants will need to be recruited per group for a total of 148 participants.

Two-Sample T-Tests Allowing Unequal Variance

Numeric Results for an Unequal-Variance T-Test

$$\delta = \mu_1 - \mu_2$$

$$\text{Hypotheses: } H_0: \delta \neq 0 \text{ vs. } H_1: \delta \neq 0$$

Target Power	Actual Power	N1	N2	N	μ_1	μ_2	δ	σ_1	σ_2	Alpha
0.80	0.80342	61	61	122	890.0	458.0	432.0	1046.0	560.0	0.050

Moderate Intensity Minutes (# of minutes in which >100 steps were accumulated): We will have sufficient power to detect differences in number of minutes of moderate intensity steps collected over 7 days via the SAM. With 74 participants per group we will have 86%

STATISTICAL ANALYSIS PLAN – WHIP-PD

power to detect an effect size of 0.5 in number of minutes of moderate intensity steps collected over 7 days via the SAM.

Two-Sample T-Tests using Effect Size

Numeric Results for Two-Sample T-Test

Alternative Hypothesis: H1: $d \neq 0$

Power	N1	N2	N	d	Effect Size	Alpha
0.2270	74	74	148	0.20	0.050	
0.8557	74	74	148	0.50	0.050	
0.9980	74	74	148	0.80	0.050	

Randomization and relevant demographics

Block randomization (to keep randomization equal throughout the study) of participants to the two treatment arms by site using Data Access Groups will be completed using the REDCap Randomization Model. Participants will also be randomized by gender and Hoehn & Yahr. The study coordinator will click a randomize button in the REDCap database for their site after confirming eligibility and obtaining consent.

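### The only specified comparison is an unadjusted t-test of change; adding the baseline value and the randomisation factors is a low-cost precision gain whose size depends on an unreported correlation

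*SAP*

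**What the plan says.** SAP section 4 defines both primary outcomes, mean steps per day and moderate intensity minutes, as change from baseline to one year. SAP section 6 then gives the only between-arm test: "The unadjusted treatment comparison will be determined using a Satterthwaite unpooled t-test to allow for unequal variance in treatment groups". For the 6MWT and 10MWT it adds: "We will use a similar approach to the analysis described above to analyze the effect of the intervention on secondary outcomes of walking capacity".

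The heading of section 4 is "ENDPOINTS AND COVARIATES", yet the section lists endpoints only. The word unadjusted suggests an adjusted counterpart, but neither document contains one. SAP section 5 allows transformation, winsorizing or nonparametric analysis if the distributions call for it; none of these is a covariate adjustment.

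SAP section 2 describes block randomisation of participants "to the two treatment arms by site using Data Access Groups" and continues: "Participants will also be randomized by gender and Hoehn & Yahr". The protocol (Primary Outcome Measure) has the activity monitor worn for seven days before the intervention starts, so the baseline value is recorded as well.

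**The concern.** A t-test of change is a regression on baseline with the slope fixed at 1. If the true slope is not 1, some variance that baseline could explain stays in the comparison. Leaving out site, gender and Hoehn & Yahr has a similar effect: if they predict change, their contribution counts as noise, and because randomisation has balanced them the unadjusted test becomes somewhat conservative. The possible loss is a wider interval than the recorded data require. The question is how much wider.

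**Working it through.** **Inputs.** All from SAP section 2 unless marked as assumed.
- Pilot steps per day, baseline SD then 12-month SD: mHealth 1046 and 1900; control 560 and 1636.
- Target difference 890 − 458 = 432. Two-sided alpha 0.05.
- 74 per arm and 20% drop-out: 74 × 0.8 = 59.2, so 59 completers per arm.
- r, the baseline to 12-month correlation: not given. Assumed equal in both arms and shown as a range.

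**The plan's own figure.** With SDs 1046 and 560 and 61 per arm, the standard error is √((1046² + 560²)/61) = √(1,407,716/61) = 151.9, and 432/151.9 = 2.84. The noncentral t with Satterthwaite degrees of freedom gives power 0.8034, which agrees with the SAP's 0.80342.

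**Change score against baseline-adjusted variance.** Write s0 and s1 for the baseline and 12-month SDs, and sum over the two arms:
- Σs0² = 1,407,716
- Σs1² = 1900² + 1636² = 6,286,496
- Σs0·s1 = 1046×1900 + 560×1636 = 2,903,560

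Then:
- Change score: V_c = Σs0² + Σs1² − 2r·Σs0·s1 = 7,694,212 − 5,807,120 r
- Pooled baseline slope: b = r × 2,903,560/1,407,716 = 2.063 r
- Baseline-adjusted: V_a = Σs1² − b·r·Σs0·s1 = 6,286,496 − 5,988,893 r²

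The 95% half-width is t × √(V/59), with t about 1.98.

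| r | b | V_a/V_c | Half-width, change vs adjusted |
|---|---|---|---|
| 0 | 0.00 | 0.82 | |
| 0.3 | 0.62 | 0.97 | |
| 0.4 | 0.83 | 0.99 | |
| 0.5 | 1.03 | 1.00 | 564 vs 564 |
| 0.6 | 1.24 | 0.98 | |
| 0.7 | 1.44 | 0.92 | 491 vs 472 |
| 0.8 | 1.65 | 0.81 | 450 vs 404 |

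Worked row, r=0.8: V_c = 3,048,516, V_a = 2,453,604, ratio 0.805. The half-widths are 1.98 × √(3,048,516/59) = 450 and 1.98 × √(2,453,604/59) = 404. The gain vanishes where b = 1, that is at r = 1,407,716/2,903,560 = 0.485, and grows on either side.

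**Equal SDs at both visits.** Per arm, V_c = 2σ²(1−r) and V_a = σ²(1−r²), so the ratio is (1+r)/2: 0.65 at r=0.3, 0.75 at 0.5, 0.85 at 0.7 and 0.90 at 0.8.

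**Finite-sample cost of the full model.** The table ignores the degrees of freedom spent on covariates and the caution built into HC3. A simulation covers both: 148 randomised, 20% random drop-out, pilot SDs, 432 steps, 4,000 runs per cell. Its assumptions are blocks of 4 within site × gender × three Hoehn & Yahr levels, split 20/60/20. Power of the HC3 model minus power of the t-test, in percentage points:

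| r | Factors explain nothing | Factors explain 10% of the variance of change (assumed) |
|---|---|---|
| 0.5 | −3 | 0 to +2 |
| 0.6 | −2 | +1 |
| 0.7 | −2 to 0 | +3 to +4 |
| 0.8 | +5 | +9 to +10 |

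Type I error for the t-test was 0.048 to 0.052 when the factors explain nothing and 0.039 to 0.040 when they explain 10%. For the HC3 model it was 0.034 to 0.047. Neither exceeds the nominal level beyond simulation error. Only the differences in power are used here.

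**The case against.** The strongest reply is that nothing is wrong. The test is prespecified and two-sided, it allows for unequal variances, and it matches both the SAP's hypothesis of greater change and the procedure used for the sample size. The benefit depends on two quantities that the documents do not give: r, and the share of variance that the randomisation factors explain. With the pilot SDs the gain is 0 to 2% of the variance at r=0.4 to 0.6, and in that range the larger model can lose a little power. All of this stands, and it is why the point is an improvement and not a correction. The match to the hypothesis is not lost, though: once baseline is in the model, the arm coefficient is the same whether the outcome is the 12-month value or the change.

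A second reply concerns high correlations. With the pilot SDs, r=0.9 gives a variance ratio of 0.58, and a reader might infer a very large loss. But the slope in each arm is r × s1/s0. At r=0.9 that is 0.9 × 1900/1046 = 1.63 in mHealth and 0.9 × 1636/560 = 2.63 in control, pooled 1.86. Each extra baseline step would have to predict more than two and a half 12-month steps in controls. That is implausible, so values above r=0.8 should carry no weight. Even at r=0.8 the control slope is 0.8 × 1636/560 = 2.34, so that row is the outer edge of the range.

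A reader might also infer that intervals will be wider for both primary outcomes and for walking capacity. The documents give no SDs for moderate intensity minutes, the 6MWT or the 10MWT, so this is not shown.

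**Conclusion.** The point holds as a missed efficiency gain. The specified test is valid, and no bias or inflated error rate is shown. For steps per day with the pilot SDs, adjustment saves close to nothing at r=0.4 to 0.6, about 8% of the variance at r=0.7, 19% at r=0.8, 3% at r=0.3 and 18% at r=0. If SDs are similar at the two visits, the saving is (1−r)/2, for example 25% at r=0.5. In large samples with 1:1 allocation the adjusted analysis is no less precise than the change score; at this trial's size it can cost about 2 to 3 points of power near r=0.5 to 0.6 if the randomisation factors explain nothing. All of this rests on an assumed r that is common to both arms.

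Two stronger readings are not supported. The half-widths above are near the 432-step target, and a reader might infer that the unadjusted test is what leaves the trial short of power. They are near or above 432 at r=0.5 to 0.7 under either analysis, and the SDs used for the sample size are a separate matter. Nor should adjustment be taken as a remedy for drop-out: the model still needs both the baseline and the 12-month week, and under some drop-out patterns it could carry somewhat more bias than the change score.

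**What to change.** - In SAP section 6, make the primary analysis of each primary outcome a linear model of the 12-month value on arm, baseline value, site, gender and Hoehn & Yahr, coded as stratified in REDCap. Use HC3 robust standard errors, which keep the allowance for unequal variances.
- List these covariates in section 4.
- Keep the Satterthwaite t-test of change as a sensitivity analysis.
- Use the same model for the 6MWT and 10MWT.
- State that the section 5 provision for transformation, winsorizing or nonparametric analysis still applies.
- Make the change before anyone sees outcome data by arm, so that the choice of covariates cannot be data-driven.

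The cost is a SAP amendment and a little programming, since every covariate is already recorded. The statistical cost is the small loss of power given in the verdict. If the sponsor prefers to keep the present test, section 4 should at least say that no covariates are used.

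### The primary test is an unadjusted t-test on change: it leaves out the randomisation factors and the intermediate SAM weeks, and drops anyone without a 12-month week

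*SAP*

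**What the plan says.** **Test.** SAP section 6 (Primary Outcome Analyses): "The unadjusted treatment comparison will be determined using a Satterthwaite unpooled t-test to allow for unequal variance in treatment groups". Section 4 defines both primary outcomes as change from baseline to one year. No other primary comparison is described.

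**Randomisation.** SAP section 2 blocks by site and adds: "Participants will also be randomized by gender and Hoehn & Yahr". Section 4 is headed "ENDPOINTS AND COVARIATES" but names no covariate.

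**SAM weeks.** The protocol (Primary Outcome Measure) schedules a week of wear after each of four assessments. That the middle two fall at 3 and 6 months is inferred from its Assessment Procedures. SAP section 3 says that SAM data "over the 7-day period at each time point will be used in analyses", yet section 6 uses only baseline and one year.

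**Missing data.** SAP section 2: "To account for 20% drop out rate, 74 participants will need to be recruited per group". Section 5: "Vigorous attempts will be made to obtain follow-up assessments on all participants, regardless of compliance with treatment protocols" and "If a participant cannot complete any of the follow-up assessments, the reason will be clearly documented". It names no estimator and no sensitivity analysis. Section 6 nevertheless says: "We will conduct the main analyses on the full sample". The SAP reference list includes a missing-data textbook, but the text neither cites it nor applies a method from it.

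**The concern.** There are two separate costs.

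The first is efficiency. Randomising within factors balances them between arms, so the true variance of the arm difference falls if they predict outcome. An unadjusted t-test does not credit that reduction. Its standard error is then too large, and its type I error and power are both lower than they need be. Subtracting baseline also fixes its slope at 1, whatever the data show.

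The second is missing follow-up. A participant without a 12-month week has no change score, so by default the test is a completers analysis. That is an inference, because the SAP never uses the term, but no other rule is given. If dropout depends on progress differently by arm, the completers contrast is biased. The SAM weeks and documented reasons that could help probe this are already planned but have no place in the analysis.

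**Working it through.** **Inputs.** Pilot SDs from SAP section 2: mHealth 1046 at baseline and 1900 at 12 months; control 560 and 1636. Difference 432 steps/day, two-sided 0.05. Evaluable n = 74 × 0.8 = 59.2, taken as 59 per arm. Correlations, variance shares and dropout rules are not in the documents and are assumed.

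**The plan's own figure.** Unequal-variance t-test power at 61 per group, difference 432, SDs 1046 and 560: 0.8034, matching the SAP's 0.80342. Those are baseline SDs. The figures below use SDs of change, so baseline power is 33% rather than 80%; that gap is a separate sample-size matter.

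**Standard error of the change contrast.** SD of change = √(SD0² + SD12² − 2r·SD0·SD12). At r = 0.5 this gives 1648 and 1440. SE = √((1648² + 1440²)/59) = 285. Power for 432 = 1 − Φ(1.96 − 432/285) = 33%.

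**Randomisation factors.** Let them explain a share R of the variance of change. With balanced strata the true SE is 285·√(1 − R).
- Unadjusted power: 1 − Φ[(1.96 − 432/285)/√(1 − R)].
- Adjusted power: 1 − Φ[1.96 − 432/(285·√(1 − R))].
- Type I error: 20,000 simulated null trials of 148, with 20% random loss. Eight strata and blocks of 4 are assumptions: the documents give no block size and no grouping of Hoehn & Yahr stages 1-3.

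| R | Unadjusted type I error | Unadjusted power | Adjusted power |
|---|---|---|---|
| 5% | 4.7% | 32% | 34% |
| 10% | 4.2% | 32% | 36% |
| 20% | 3.3% | 31% | 40% |

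A separate run at R = 10% to 20% gave type I error of about 3.4% to 3.8%, with power rising from about 30-32% to 35-38%.

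**Baseline.** Common slope b = Σ(r·SD0·SD12)/ΣSD0². Adjusted variance per arm = SD12² − 2b·r·SD0·SD12 + b²·SD0². At r = 0.3:
- b = 0.3 × 2,903,560/1,407,716 = 0.619.
- Sum over arms: 5,747,496 adjusted against 5,952,076 for change; ratio 0.966.

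The ratios at r = 0.1 to 0.7 are 0.875, 0.926, 0.966, 0.992, 1.000, 0.981 and 0.924. The saving is 0% to 12%, only 0% to 3% at r = 0.3 to 0.6, and adjustment is never worse at the values checked.

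**Completers-only shift.** Assume 20% loss per arm, r = 0.5 from baseline, 6-to-12-month r = 0.7, equal 6- and 12-month SDs, and poorer 6-month change raising the odds of dropout by 1.65 or 2.7 per SD. The mean standardised 6-month change among those retained is then 0.0963 or 0.1724. Shift = cov(12-month change, 6-month change)/SD(6-month change) × that mean.
- mHealth: (0.7·1900² − 1046·1900 + 1046²)/1648 = 1,633,716/1648 = 991, giving +95 or +171.
- Control: 1,270,987/1440 = 883, giving −85 or −152 on the contrast.

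| Dropout pattern | Shift (steps/day) | Two-sided type I error |
|---|---|---|
| Same rule, both arms | +10 or +19 | about 5.0% |
| Odds ratio 1.65 mHealth, 2.7 control | −57 | 5.5% |
| mHealth only, control random | +95 or +171 | 6.3% or 9.2% |
| Control only, mHealth random | −85 or −152 | 6.0% or 8.3% |

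A separate simulation under other assumptions (SD 1500 at every wave, low month-6 walkers dropping out in mHealth only) gave +21 to +59 under the null, with type I error of 4.9% to 5.2%.

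**Would a missing-at-random model remove the shift?** It depends on what drives dropout. One-arm shifts in absolute size, odds ratio 1.65:

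| Driver of dropout | Completers | Missing-at-random estimate |
|---|---|---|
| 6-month change, all dropouts have a 6-month week | 95 (mHealth), 85 (control) | within about 2 |
| 12-month change | 157, 140 | 102, 89 |
| Decline after month 6 | 71, 60 | about 113, 97 |

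In the first row, about 44-45% of the shift remains if half the dropouts have a 6-month week, and all of it if none do.

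**The case against.** The planned test is orthodox. It matches the endpoint, the baseline-to-12-month comparison named in the protocol, and the sample-size method. The plan chases follow-up regardless of compliance and records reasons, and the protocol allows repeat wear for unusable data or damaged devices. The word unadjusted may imply an adjusted counterpart, and the textbook reference suggests that missing data were considered. The large shifts need progress-related dropout in one arm and random dropout in the other.

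Most of this stands as a limit on size. It does not close the gap. Repeat wear does not cover dropout, no adjusted analysis is described, and no missing-data method is applied.

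A reader might make three stronger inferences that the documents do not support.
- *That the trial would understate the intervention, because only mHealth has a phone call after a lapse.* That call responds to app login, not SAM return. The protocol plans no interactions in months 7-12, and the SAP says that none will occur, so the call may not operate then. Control has the same number of visits, plus journals and a phone number. No direction follows.
- *That the t-test inflates type I error.* With complete data it does not; it is conservative if the factors matter.
- *That a repeated-measures model would cure the bias.* If dropout follows decline after month 6, it does worse than completers.

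**Conclusion.** The concern holds as a should-fix improvement; the planned test is not invalid. The firm part can be read from the SAP: factors used to randomise, two planned SAM weeks and participants without a 12-month week have no role in the only stated primary test, and the full-sample wording conflicts with that test.

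The gain from adjusting for the randomisation factors is about 3 to 9 power points if they explain 10% to 20% of the variance, and smaller below that. Baseline adjustment adds little at mid-range correlations. Completers-only bias ranges from negligible to over 100 steps/day, depending wholly on assumed dropout patterns. All figures rest on pilot SDs and assumed correlations, and none covers moderate-intensity minutes.

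**What to change.** 1. For both primary outcomes, make the primary comparison a baseline-adjusted model with site, gender and Hoehn & Yahr and arm-specific or robust variance, which keeps the unequal-variance intent. Use the same covariates for the 6MWT and 10MWT. List them in section 4 and keep the Satterthwaite t-test as supportive.
2. Pre-specify in section 5 a repeated-measures model using all collected SAM weeks. State that it relies on missing-at-random and does not guarantee less bias than completers.
3. Add a tipping-point analysis that imputes every randomised participant lacking a 12-month week, including those with no post-baseline week, and varies the shift separately by arm until the conclusion changes. A fixed cap could be too narrow: with 20% imputed, 432 per dropout moves an arm mean by only 0.20 × 432 = 86, and covering a shift of 171 needs 171/0.20 = 855. Tabulate missing weeks and reasons by arm.
4. Reconcile the full-sample statement with the stated test.

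The cost is SAP wording, a few degrees of freedom and a little more analysis work. No data are needed beyond those already planned.

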COVER PAGE

PROTOCOL

Official Title: Walking and mHealth to Increase Participation in Parkinson Disease

NCT Number: NCT03517371

Document Date: July 12, 2023

PROTOCOL AND CONTACT INFORMATION

Protocol Number (To be assigned by IRB Office):	4854E
Protocol Title:	Walking and mHealth to Increase Participation in Parkinson Disease (WHIP-PD)
Principal Investigator (Name, degrees, licenses, etc.):  Mr.  [name], PhD, PT, NCS (Boston University) [name], PT (Washington University in St. Louis)
Department/School:	Physical Therapy & Athletic Training / Sargent
BU Mailing Address:	[name]
Email:	[contact]
[contact]
Additional Contact Person:	
Email:	
Telephone:	

STUDY SUMMARY

Objectives/Aims

Parkinson disease (PD) is one of the most disabling chronic health conditions affecting older adults globally. Of particular concern is walking decline, which is considered a red flag signaling emerging disability. The primary factors that limit engagement in walking in PD are psychological (e.g., low self-confidence) rather than physical (e.g., movement impairments) in nature. We will evaluate an approach targeted at enhancing walking activity by addressing not just movement but also psychological factors. Our “connected behavioral approach” links physical therapists to persons with PD using a mobile health (mHealth) platform that incorporates strategies to increase self-confidence and provides goal-oriented, dynamic walking routines and exercises to enhance walking over the course of one year. We will compare this approach to a control intervention which provides equivalent components and dosing of walking and exercises to enhance walking delivered by physical therapists but without using mHealth.

Specific Aims and Hypotheses:

Primary Aims: Determine if our “Connected Behavioral Approach” is more effective than an active control in increasing real-world walking activity in persons with PD. **Hypothesis 1:** Participants in the mHealth arm will accumulate **(1a)** more daily steps (Step Activity Monitor worn in the free-living environment) and **(1b)** more moderate intensity steps (# of minutes of >100 steps) at 1 year compared to an active control condition.

Secondary Aims: Determine if our “Connected Behavioral Approach” is more effective than an active control condition in improving walking capacity in persons with PD. **Hypothesis 2:**

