1 ANALYSIS OBJECTIVES

Hypotheses/Aims

Aim 1: Determine if “Connected Behavioral Approach” is more effective than an active exercise control in increasing real-world walking activity in persons with PD.

Hypothesis 1: Participants in the mHealth arm will have greater change in (1a) daily steps (Step Activity Monitor (SAM) worn in the free-living environment) and (1b) moderate intensity minutes (number of minutes in which participants walk greater than 100 steps per minute per day) between baseline and 12-months compared to the active exercise control condition.

Aim 2: Determine if our “Connected Behavioral Approach” is more effective than an active exercise control condition in improving walking capacity in persons with PD.

Hypothesis 2: Participants in the mHealth arm will have greater change in walking capacity (6-min walk test, 10-meter walk test) between baseline and 12 months compared to the active exercise control arm.

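### Two primary outcomes under one aim are each tested at two-sided 0.05, and no rule says how the two results decide the aim

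*SAP*

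**What the plan says.** SAP section 1 gives a directional Aim 1: whether the approach "is more effective than an active exercise control in increasing real-world walking activity in persons with PD". Hypothesis 1, under that aim, predicts "greater change in (1a) daily steps (Step Activity Monitor (SAM) worn in the free-living environment) and (1b) moderate intensity minutes". The protocol's Hypothesis 1 pairs daily steps in the same way with "more moderate intensity steps (# of minutes of >100 steps) at 1 year compared to an active control condition".

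SAP section 4 uses the plural: "The primary outcomes are the change from baseline to one year in mean number of steps per day over a seven-day period", and then adds moderate intensity minutes without ranking the two. SAP section 6 states a single purpose, "Our primary aim is to determine effectiveness of the intervention to improve walking behavior at one year", assigns the same unequal-variance t-test to both outcomes, and sets the level: "The two-sided 0.05 level will be used for significance in all analyses". A further line giving 0.05 two-sided per hypothesis stands under Secondary Outcome Analyses.

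SAP section 2 treats the outcomes separately. For steps, "group sample sizes of 61 participants per group will be needed to achieve 80% power". For moderate intensity minutes it states 86% power at d = 0.5 with 74 per group. Neither document gives a testing order, an alpha split, a joint power, or a statement that one or both outcomes must be significant.

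**The concern.** A primary aim with two outcomes needs a rule that turns two p-values into one conclusion. Three rules fit the text: either outcome suffices, both are required, or the two are separate claims with no combined verdict. They have different error rates and different power, and the SAP does not choose among them. If one outcome is significant and the other is not, the reading could be settled after the results are known. The error rate or power behind the primary claim would then differ from what the SAP leads a reader to expect.

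**Working it through.** **Inputs (SAP section 2).** Steps: changes 890 and 458, difference 432, SDs 1046 and 560, 61 per group, two-sided 0.05. Moderate intensity minutes: d = 0.5 (also tabulated: 0.2 and 0.8), 74 per group, two-sided 0.05. The correlation between the two test statistics is not in the documents, so it is varied from 0 to 1 as an assumption.

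**1. Reproduce the stated powers.**
- 1a: SE = √((1046² + 560²)/61) = 151.9; noncentrality 432/151.9 = 2.84; Satterthwaite df 91.8; power 0.8034 (SAP: 0.80342).
- 1b: noncentrality 0.5 × √(74/2) = 3.04; power 0.8557 (SAP: 0.8557).

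Both reproduce at the full 0.05. At 0.025 each they would be 71.3% (61 per group) and 78.0% (74 per group), so no alpha split is built into the sample size.

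**2. Put both outcomes on the same sample.** At 61 per group and d = 0.5, 1b has noncentrality 0.5 × √(61/2) = 2.76 and power 0.7821. The step from 86% to 78% comes only from counting completers instead of all recruited participants.

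**3. Work through the readings** (bivariate normal for the two test statistics).
- Either suffices, no true effect: at correlation 0 the error is 1 − 0.95² = 9.75% two-sided and 1 − 0.975² = 4.9% favouring mHealth. At correlation 1 these fall to 5% and 2.5%, the values for a single test.
- Both required: joint power is the probability that both are significant; at correlation 0 it is 0.8034 × 0.7821 = 0.628.
- Exactly one significant: 0.8034 + 0.7821 − 2 × joint power.

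| Assumed correlation | Either suffices: two-sided error | Either suffices: favouring mHealth | Joint power (61 per group, d = 0.5) | Exactly one significant (d = 0.5) |
|---|---|---|---|---|
| 0 | 9.75% | 4.9% | 62.8% | 32.9% |
| 0.5 | 9.1% | 4.5% | 67.7% | 23.2% |
| 0.8 | 7.8% | 3.9% | 72.0% | 14.6% |
| 0.9 | 7.0% | 3.5% | 74.1% | 10.4% |
| 1 (limit) | 5.0% | 2.5% | 78.2% | 2.1% |

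In the last row, joint power is the smaller of the two powers, and the split is 0.8034 − 0.7821 = 0.021.

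With the SAP's other tabulated effects for 1b, exactly one outcome is significant in 61%-69% of trials (d = 0.2) or 19%-20% (d = 0.8).

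**4. Cost of candidate rules** (61 per group, correlation 0 to 0.9; Holm and Hochberg by simulation of 2,000,000 draws).
- Fixed sequence, 1a then 1b: 1a keeps 80%. 1b is confirmed only when both are significant, so its confirmatory power equals the joint power, 63%-74% at d = 0.5.
- Holm, d = 0.5: 1a 75%-78%, 1b 74%-76%.
- Hochberg, d = 0.5: 1a 77%-79%, 1b 76%.
- Holm or Hochberg, d = 0.2: 1a about 72%-73%.

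**The case against.** The strongest reply is that 1a and 1b are two separately reported outcomes. The SAP labels them individually, powers each alone and applies 0.05 throughout. On that reading neither test has an inflated error rate, and neither document promises a single win-or-lose verdict. This stands as far as it goes: error inflation is not established. But section 6 states one aim and Hypothesis 1 holds both outcomes, so a split result still leaves the aim unanswered.

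A second reply is that a rule is implied.
- The word joining 1a and 1b may mean that both are required, but it may equally just list them, and no joint power is given.
- Steps might seem to lead: the protocol's outcome heading is singular, the text below it concerns step counts and speaks of a primary comparison, and the trial was sized on steps. That comparison identifies the time window (the week before the intervention against the week after month 12), not a ranking of steps over minutes. Sizing on one outcome is not a testing order.

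Third, the SAP's reference list includes a paper on multiplicity that the text never cites. A reader might infer that a rule exists in a fuller plan. The documents cannot settle that, and a title supplies no rule. The finding is therefore about the supplied text.

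Finally, the protocol is dated July 2023 and expects 12-month assessments through December 2023, so a change may come late. The documents do not say whether results have been seen.

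**Conclusion.** The concern holds in a limited form: the supplied text gives no rule for drawing the primary conclusion from two outcomes, each tested at the full two-sided 0.05. This does not depend on the correlation or on the reading chosen.

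The size does depend on them. A reader might infer that the trial's false-positive rate is 9.75%. The documents do not support that: it is the upper end of a 5% to 9.75% range, reached only if either outcome suffices and the tests are independent. A reader might also take 10% as the least likely frequency of a split result. That figure belongs to correlation 0.9; at d = 0.5 the frequency falls to about 2% near correlation 1. If both outcomes are required, error stays within 5%, but joint power is 63% to 74% (correlation 0 to 0.9), below the separately stated 80% and 86%. All the power figures take the SAP's own effects and 61 completers per group, and d = 0.5 for 1b is an illustrative effect, not a pilot estimate.

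The point is worth acting on because it concerns the primary conclusion and costs little to settle.

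**What to change.** Before unblinded results are seen, replace the blanket 0.05 rule for the primary outcomes in SAP section 6 with a fixed sequence. For example: *Steps per day (1a) will be tested at two-sided 0.05. Moderate intensity minutes (1b) will be tested at two-sided 0.05 as confirmatory only if 1a is significant; otherwise 1b will be reported as exploratory.* Steps goes first because the trial was sized on it. The chance of any false positive across the pair is then held at 5%, because a non-significant 1a stops confirmatory testing.

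Cost: one or two sentences, with no extra participants or data. 1a keeps its 80% power. The price falls on 1b, whose confirmatory power at d = 0.5 drops from 78% to about 63%-74%, and which cannot be claimed if 1a misses.

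If the sponsor wants the outcomes co-equal, Holm or Hochberg is the alternative. It costs 1a a few points at d = 0.5 (to about 75%-79%) and more at the SAP's tabulated d = 0.2 (to about 72%-73%).

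If results have already been seen, a rule can no longer be called pre-specified, and the report should say so.
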